8.2.9. Other Safety Analysis

Clopidogrel Analysis

The following analyses will be conducted to confirm the effect of clopidogrel co-administration.

The treatment emergent AEs and SAEs will be summarized with the number, percentage and rate per 100 person-years, by clopidogrel co-administration, treatment group, and system organ class and preferred term. Clopidogrel co-administration is defined as subjects who use clopidogrel once or more during the on-treatment state for concomitant medications (see Section 10.4.1).

The number and percentage of subjects with a >1 g/dL increase in Hgb over 2 weeks (assessed at Week 2 and Week 4), or a >2 g/dL increase in Hgb within any 4-week period from Week 4 to Week 52, will be summarized by visit by clopidogrel co-administration, and by treatment group using HemoCue Hgb values. This summary will be presented using evaluable Hgb values only (see Section 10.6.3).

The number and percentage of subjects with a >2 g/dL increase in Hgb within any 4-week period from Week 4 to Week 52, will be summarized by visit by clopidogrel co-administration, and by treatment group using central laboratory Hgb values. This summary will be presented using evaluable Hgb values only (see Section 10.6.3).

For the above two tables, the Clopidogrel co-administration groups are baseline clopidogrel users, new clopidogrel users, and clopidogrel non-users during the first year of the study. Baseline clopidogrel users, defined as subjects who use clopidogrel at randomization, will be summarized only at Week 2 and Week 4 for the HemoCue Hgb table, and only at week 4 in the central laboratory Hgb table. New clopidogrel users are defined as subjects who started clopidogrel after randomization during the on-treatment state for concomitant medications (see Section 10.4.1) in the first year of the study. If they started clopidogrel within two weeks of a scheduled visit (i.e. visit date - 2w < clopidogrel start date \leq visit date + 2w), they will only be summarized in the following scheduled visit. Clopidogrel non-users are subjects who do not use clopidogrel neither at randomization nor anytime during the on-treatment state for concomitant medications (see Section 10.4.1) in the first year of the study.

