A box plot of evaluable Hgb change at Week 2 from baseline, by baseline clopidogrel co-administration and treatment group will be produced. Baseline clopidogrel co-administration is defined as subjects who use clopidogrel at randomization. Hemocue Hgb will be used in this figure, since only Hemocue Hgb is available at Week 2. This box plot will be repeated at Week 4 using evaluable Hgb, by baseline clopidogrel co-administration and treatment group.

A box plot of 4-week changes in evaluable Hgb after starting clopidogrel will also be produced by treatment for new clopidogrel users, who started clopidogrel after randomization, during the on-treatment state for concomitant medications (see Section 10.4.1). The 4-week change in evaluable Hgb will be estimated by calculating the change at the first visit after starting clopidogrel, from the previous visit at least 4 weeks before. The first visit after starting clopidogrel is defined as the first visit (scheduled or unscheduled) after clopidogrel start that was at least two weeks after the start date of clopidogrel.

COVID-19 Analyses

The following COVID-19 related displays will be provided.

A summary of the number and percentage of subjects for the following assessments will be produced: Case Diagnosis, COVID-19 Test performed, and Results of the COVID-19 test.

Summaries of characteristics of COVID-19 AEs will include the number, percentage of subjects having at least one occurrence, the outcome, maximum intensity, and the duration of the AE summarized by treatment group. For each count, a subject will be summarized as follows:

- Outcome: The subject will be counted within a category if there is at least one specific AE in that category.
- Maximum intensity: The specific AE with the maximum intensity will be counted for this purpose. For example, a subject will be counted in the ‘severe’ category if there is at least one specific AE with severe intensity. A subject will be counted in the ‘moderate’ category if there is at least one specific AE with moderate intensity and there is no specific AE with severe intensity.
- Duration of the occurrence (days): AE resolution date – AE onset date/AE worsening date + 1 for the occurrence

A summary of the number and percentage of subjects with COVID-19 symptoms will be produced.

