10.2. Appendix 2: Time & Events

10.2.1. Protocol Defined Time & Events

10.2.1.1. Schedule of Assessments Year 1 to the End of the Study

Protocol activity (visits ±1 week, except Weeks 2 and 4 which are ±3 days) (Note: All visit timings are relative to Day 1)	Screen Week -8	Run-in Week -4	Day 1 through Week 52					
			Day 1 ¹³	Week 2	Full study visit Week 4, 16, 28, 40	Abbreviated study visit Week 8, 12, 20, 24, 32, 36, 44, 48	Week 52	Unscheduled ¹⁰
Informed Consent (main study)	X ²⁰							
IRT system transaction	X	X	X	X	X	X	X	X
Subject reminder, inform site staff of changes in health ¹			X				X	
Check/confirm entry criteria, weight	X		X					
History: medical, hospitalization, transfusion demography, height	X							
SBP/DBP, HR (single readings unless otherwise indicated)	X	X	X (triplicate)	X	X	X	X (triplicate)	X
ECG			X ¹⁷				X	
Ultrasound of kidneys and adrenal glands		X ¹⁶						
Placebo run-in or randomized treatment dispensing (start administration on day of dispensing)		X (placebo)	X	X ⁹	X	X	X	X ⁹
Placebo run-in or randomized treatment compliance			X (placebo)	X ¹¹	X	X	X	X ¹¹
Iron therapy, transfusions ²	X	X	X	X	X	X	X	X
Rescue medication(s) for Initial Intervention ^{2,3}					X	X	X	
Females only: estradiol and FSH (if required)	X							
FRP only: urine pregnancy test ^{4,18}		X	X		X		X	
HemoCue Hgb	X	X	X	X	X	X	X	X
Hematology ⁵	X	X	X		X	Hgb only	X	X
Clinical chemistry ⁵	X		X		X		X	X
Ferritin, total iron, UIBC ⁵	X		X		X		X	
Hepcidin			X		X		X	
HbA1c ⁶ , lipids (non-fasting)			X				X	
hsCRP, iPTH			X		Wk 28		X	
Urine albumin/ creatinine ratio			X		Wk 4, Wk 28		X	

CONFIDENTIAL

200808

Protocol activity (visits ±1 week, except Weeks 2 and 4 which are ±3 days) (Note: All visit timings are relative to Day 1)	Screen Week -8	Run-in Week -4	Day 1 through Week 52					
			Day 1 ¹³	Week 2	Full study visit Week 4, 16, 28, 40	Abbreviated study visit Week 8, 12, 20, 24, 32, 36, 44, 48	Week 52	Unscheduled ¹⁰
Storage biomarkers (blood, urine) ¹⁹			X		Wk 28		X	
Hospitalization ² , transition to dialysis ^{2,7} , kidney transplant ²				X	X	X	X	X
Non-serious AEs, SAEs, AEs of special interest, clinical events	X ⁸	X	X	X	X	X	X	X
Review concomitant medications	X	X	X	X	X	X	X	X

Schedule of Assessments Year 1 to End of Study (Continued)

Protocol activity (visits ±1 week) (Note: All visit timings are relative to Day 1)	Year 2				Year 3				Year 4					Unscheduled ^{10,12}	End of Study ¹⁵	Follow-up (4-6 weeks after stopping randomized treatment)	

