4. Repeat pregnancy test prior to placebo run in or randomized treatment re-administration if it is disrupted for >7 days and there was also a lapse in contraceptive use, regardless of the reason for the disruption. If a subject becomes post menopausal (as defined in Protocol Appendix 6) during the study pregnancy tests are no longer required.
5. See details on hematology and clinical chemistry in Protocol Section 7.4.11.
6. HbA1c assessment only in subjects with diabetes on Day 1 or diagnosed during the study.
7. Subjects transitioning to dialysis must follow the time and events schedule detailed in Protocol Appendix 7. See also Protocol Section 6.13 for additional details.
8. Only SAEs assessed as related to study participation or a GSK product are collected at this visit. See Protocol Section 7.4.3.1 for additional details.
9. If dose does not change, then randomized treatment is returned to subject.
10. If a subject lost their placebo run in or randomized treatment, it is not necessary to perform the unscheduled visit assessments other than dispensing randomized treatment.
11. Required only if dose is changed or randomized treatment is dispensed. Compliance checking will be required when a dose of randomized treatment is changed.
12. Additional visits to check Hgb and dispense randomized treatment (where directed by the IRT system) are required under the circumstances described in Protocol Appendix 5. Hematology and chemistry samples are not required.
13. All assessments pre-dose.
14. Further visits every 12 weeks as required.
15. Investigator will inform subject when to attend this End of Study visit (Protocol Section 6.3.4).
16. Ultrasound of the kidneys and adrenal glands will be performed as early as 6 weeks prior to the Day 1 visit. If results of kidney and adrenal ultrasound require follow-up testing, then the run-in period can be extended by 1 additional week. A documented ultrasound of the kidneys within the 6 months prior to screening may be used to assess entry criteria, provided the size and cyst category has been reported. If a more sensitive imaging study [e.g., magnetic resonance imaging (MRI), computed tomography.(CT)] has been performed within this timeframe and a report is available, this may be used in place of the ultrasound.. See Protocol Section 7.4.10.
17. Day 1 ECG may be performed as early as the Week – 4 visit through the Day 1 visit; If performed on Day 1, it must be over-read prior to randomization.

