10.6.2.4. Prior and Concomitant Medications

Prior and Concomitant Medications
Non-randomized ESA use during treatment period

 • Subjects will be considered to have non-randomized ESA use during the treatment period if they have any ESA concomitant medication records with one of the following two reasons for medication: 
 ○ Non-randomized ESA treatment in addition to randomized treatment ○ Non-randomized ESA treatment instead of randomized treatment
Duration of non-randomized ESA use during treatment period

 • If there is only one concomitant medication record of non-randomized ESA use during the treatment period, then: 
 ○ Duration (days) = earliest of (concomitant medication record end date, last non-zero dose date + 1 day) – latest of (concomitant medication start date, treatment start date) + 1 day • If there are multiple concomitant medication records of non-randomized ESA use during the treatment period, then the duration of non-randomized ESA use will add the durations for all records, subtracting any overlapping days that may exist between the multiple records.
Clopidogrel start date for new clopidogrel users

 • New clopidogrel users are subjects who did not use clopidogrel on randomization day, but started their clopidogrel use after randomization during the on-treatment state for concomitant medications. To determine the start date of clopidogrel for the new users, only the first clopidogrel record during the on-treatment state for concomitant medications will be considered. The start date will be the first day subjects on both clopidogrel and randomized treatment.

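### The 'before' Hgb for new clopidogrel users can be taken up to 13 days after clopidogrel started, and the '4-week' change has no upper limit on its interval

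*SAP*

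**What the plan says.** Section 8.2.9 (Clopidogrel Analysis) lists displays meant to confirm the effect of taking clopidogrel with randomized treatment. One of them reads: "A box plot of 4-week changes in evaluable Hgb after starting clopidogrel will also be produced by treatment for new clopidogrel users". Its two time points are set as follows.

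- The 'after' visit is the first visit, scheduled or unscheduled, "after clopidogrel start that was at least two weeks after the start date of clopidogrel".
- The change is estimated by "calculating the change at the first visit after starting clopidogrel, from the previous visit at least 4 weeks before".

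Section 10.6.2.4 defines who is included: "New clopidogrel users are subjects who did not use clopidogrel on randomization day, but started their clopidogrel use after randomization", while in the on-treatment state. It sets no calendar limit. The two tables of Hgb increases in Section 8.2.9 are confined to the first year of the study; the box plot does not repeat that limit.

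The visit schedule is in Section 10.2.1.1. Full visits at Weeks 4, 16, 28 and 40 and abbreviated visits at "Week 8, 12, 20, 24, 32, 36, 44, 48" give a 4-weekly grid up to Week 52. After that, visits are at Weeks 64, 76 and so on to Week 208, then "Further visits every 12 weeks as required".

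**The concern.** A change after starting a drug needs a reference value from before the drug. Here the reference is found by counting back from the 'after' visit, so it can land on a visit at which the subject was already taking clopidogrel. Any Hgb movement between the start and that visit is then subtracted out.

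The rule also sets a minimum interval but no maximum. Where visits are 12 weeks apart, a change over 12 weeks enters a plot labelled as 4-week changes, beside true 4-week changes.

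This plot is the display of within-subject Hgb change for subjects who start clopidogrel during the trial. If it is diluted and mixes intervals, a real effect would look smaller or less consistent than it is.

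**Working it through.** **Inputs.** The rule is from Section 8.2.9 and the visit days from Section 10.2.1.1: every 28 days from Week 4 (day 28) to Week 52 (day 364), then every 84 days (day 448, 532 and so on). The SAP gives no distribution of clopidogrel start dates. Where a percentage is shown, I assume that starts are spread evenly over days and that visits fall on schedule.

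**Rule as written.** Let S be the start day.

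- 'After' visit: P = first visit with P ≥ S + 14.
- Reference: R = last visit with R ≤ P − 28.

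**Year 1.** Let V be the next scheduled visit after S, and k = V − S.

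- k = 1 to 13: V is less than 14 days after S, so P = V + 28 and R = V. The reference is k days **after** the start.
- k = 14 to 28: P = V and R = V − 28, which is on or before S. This is the intended comparison.

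So 13/28 = 46% of start days have a reference taken on clopidogrel, and 15/28 = 54% do not. The lag runs from 1 to 13 days, with mean (1 + 2 + … + 13)/13 = 91/13 = 7 days. The interval P − R is 28 days in both cases.

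Example: visits on days 140, 168 and 196, with a start on day 155. Then S + 14 = 169, P = 196, and R = 168, which is 13 days after the start. A start one day earlier (day 154) gives P = 168 and R = 140, as intended.

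**Around and after Week 52, scheduled visits only.**

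- Start on days 351 to 363: S + 14 is 365 to 377, so P = 448 (Week 64) and R = last visit up to day 420 = 364 (Week 52). The interval is 84 days (12 weeks), and the reference is after the start.
- Start on day 400: P = 448, R = 364, interval 84 days.
- Start on day 445: P = 532, R = 448, interval 84 days, with the reference 3 days after the start.
- In general, after Week 52 every scheduled-visit interval is 12 weeks, and 13/84 = 15% of start days have a post-start reference.

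**Other reading.** If the 4 weeks are counted back from the clopidogrel start instead of from the 'after' visit, no reference falls after the start. Over start days 28 to 335 the interval is then 8 weeks for 53% and 12 weeks for 42%, with a few at 6 or 10 weeks. After Week 52 it is 12 to 24 weeks. Neither reading gives a pre-start to post-start change over 4 weeks for all subjects.

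**Check of the proposed reference.** Let R* = last visit on or before S, with P unchanged. For k = 1 to 13, R* = V − 28 and P = V + 28, an interval of 56 days. For k = 14 to 28, the interval is 28 days. Over start days 28 to 335 (11 cycles of 28 = 308 days), 11 × 15 = 165 (54%) have a 4-week interval, 11 × 13 = 143 (46%) have an 8-week interval, and none has a post-start reference.

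**The case against.** The strongest reply is that this is one descriptive box plot with no test or decision rule, and the SAP itself calls the change an estimate. The adverse event tables, the counts of Hgb at or above 12 g/dL, the dose-adjustment summaries and the baseline-user box plots at Weeks 2 and 4 do not use this rule. That stands, and it sets the weight of the point.

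Four stronger readings are tempting, and the SAP does not support them.

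- **That the plot cannot show an interaction.** On scheduled Year 1 visits about 54% of start days give a true pre-start value and a 4-week interval. Even a reference taken 7 days after the start leaves 28 further days of exposure in the change.
- **That the visit window breaks the Year 1 interval.** Visits are allowed "visits ±1 week, except Weeks 2 and 4 which are ±3 days", so on actual dates two visits may be 27 days apart and the reference would skip back to about 8 weeks. But Section 10.5.3 uses planned time relative to randomization for figures and derived parameters unless stated otherwise. On planned time the Year 1 visits are exactly 4 weeks apart. Percentages that depend on day-level visit variation are therefore not relied on here.
- **That every interval after Week 52 is at least 12 weeks.** Unscheduled visits count as 'after' visits. With a start on day 400 and an unscheduled visit on day 420, the reference is day 364 and the interval 56 days. Twelve weeks is the usual result, not a minimum.
- **That the new-user tables need the same change.** For starts near a visit, "they will only be summarized in the following scheduled visit", so a start shortly before a visit has its 4-week rise counted from that visit. But the relevant endpoint is a rise of more than 2 g/dL within a 4-week period, shared with non-users in the same table. A start-anchored reference would alter it for new users alone and spoil the comparison.

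**Conclusion.** The rule is badly fixed in two respects. The reference need not precede the clopidogrel start: on the Year 1 schedule this affects 13 of 28 start days, by up to 13 days. Nor is there any upper limit or first-year limit, so starts after Week 52 or in the 13 days before it usually yield 12-week changes under a 4-week label.

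The 46% rests on evenly spread starts and on-schedule visits, and on counting the 4 weeks back from the 'after' visit, which is the natural reading. The loss in g/dL cannot be given, because the SAP states no time course for the effect and no number of new users. The plot is diluted and mixes intervals; it is not uninformative. Severity is minor.

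**What to change.** Reword the box-plot derivation in Section 8.2.9 along these lines:

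- Reference: the last evaluable Hgb on or before the clopidogrel start date.
- 'After' value: the first evaluable Hgb at least two weeks after the start, as now.
- Scope: 'after' visits up to and including Week 52. Limiting the 'after' visit instead of the start date keeps out starts on days 351 to 363, whose next scheduled 'after' visit is Week 64.
- Label: drop the fixed 4-week description. Report the actual interval or group the boxes by it (about 4 or 8 weeks on schedule).

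Do not rescale the change to 4 weeks. That would assume a linear Hgb course, although doses in both arms are adjusted by algorithm to hold Hgb at 10-11 g/dL. Leave the 4-week endpoint of the two Hgb-increase tables as it is.

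The cost is a change of wording and a small derivation on data already collected. In return, intervals differ between subjects and must be shown: on schedule about 46% become 8 weeks. Subjects who start too late to have an 'after' visit by Week 52 drop out of this plot.

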8.3. Patient Reported Outcomes Analyses

This study includes the following patient reported outcomes (PROs) that are assessed according to the schedule in the Time and Events table in Section 10.2.1:

- SF-36
- EQ-5D-5L & EQ-VAS
- PGI-S
- PGI-C

- CKD-AQ
- WPAI

Additional details on these questionnaires can be found in Section 10.6.5. All analyses will use on-treatment values only unless otherwise specified.

8.3.1. Overview of Planned Patient Reported Outcomes Analyses

Table 13 provides an overview of the planned patient reported outcomes analyses.

Table 13 Overview of Planned Patient Reported Outcomes Analyses

Endpoint	Analysis Population	Absolute						Change from Baseline									
		Stats Analysis			Summary			Individual		Stats Analysis			Summary			Individual	
		T	F	L	T	F	L	F	L	T	F	L	T	F	F	L	
HRQoL and Utility Scores																	
SF-36 domain and component scores	ITT				Y					Y	Y		Y				
EQ-5D-5L & EQ VAS	ITT				Y					Y	Y		Y				
Symptom Severity																	
PGI-S score	ITT				Y					Y	Y		Y				
PGI-S categories	ITT												Y				
PGI-C categories	ITT				Y												
CKD-AQ domain and single item scores	ITT				Y					Y	Y		Y				
Work Productivity and Regular Daily Activity Impairment																	
WPAI-ANS-CPV Summaries					Y								Y				

NOTES:

- T = Table, F = Figure, L = Listing, Y = Yes display generated.
- Stats Analysis = Represents TFL related to any formal statistical analyses (i.e. modelling) conducted.
- Summary = Represents TFL related to any summaries (i.e. descriptive statistics) of the observed raw data.
- Individual = Represents FL related to any displays of individual subject observed raw data.

8.3.2. Planned Patient Reported Outcomes Statistical Analyses

8.3.2.1. HRQoL and Utility Score

Patient Reported Outcomes Statistical Analyses: HRQoL and Utility Score
Secondary Endpoints Endpoint(s)

 • Mean change in SF-36 HRQOL scores (PCS, MCS and 8 health domains) between baseline and Weeks 8, 12, 28, 52, of particular interest are the changes from baseline in the vitality and physical functioning domains at Weeks 28 and 52 • Change from baseline in Health Utility (EQ-5D-5L) score at Week 52 • Change from baseline in EQ VAS at Week 52
Exploratory Endpoint(s)

 • Change from baseline in Health Utility (EQ-5D-5L) score at Weeks 8, 12, 29, 52, yearly, EOS • Change from baseline in EQ VAS at Weeks 8, 12, 28, 52, yearly, EOS
Model Specification

 • Scoring for the SF-36 parameters and EQ-5D parameters is outlined in Section 10.6.5. • The mean change from baseline in SF-36 HRQoL scores (PCS, MCS, and 8 health domains), EQ-5D-5L score, and EQ VAS score will be analyzed using an MMRM approach with an unstructured covariance matrix to compare the difference in means between arms. The models will be fitted to QoL data collected after baseline up to Week 52. The model will include factors for treatment, time, prognostic randomization stratification factors, baseline QoL parameter value and the baseline QoL parameter by time and treatment by time interaction terms. Analyses will be done with the MIXED procedure in SAS, using the Kenward-Roger option to estimate denominator degrees of freedom and standard errors.
Model Results Presentation

 • SF-36 domain scores (PCS, MCS, and 8 health domains) will be summarized using mean, standard deviation, minimum, P25, median, P75, and maximum by treatment group at all scheduled visits. • Change from baseline in SF-36 domain scores (PCS, MCS, and 8 health domains) will be summarized using mean, standard deviation, minimum, P25, median, P75, and maximum by treatment group at all scheduled visits. • Bar graphs displaying mean change from baseline for the Week 8, 12, 28, and 52 visits for the SF-36 PCS, MCS, and 8 health domains will be provided by treatment group. • EQ-5D-5L responses will be summarized by dimension at all scheduled visits, including the derived end of treatment visit. • EQ-5D-5L and EQ VAS scores will be summarized using mean, standard deviation, minimum, P25, median, P75, and maximum by treatment group at all scheduled visits, including the derived end of treatment visit. • Change from baseline in EQ-5D-5L and EQ VAS scores will be summarized using mean, standard deviation, minimum, P25, median, P75, and maximum by treatment group at all scheduled visits, including the derived end of treatment visit. • Bar graphs displaying mean baseline and Week 52 visit scores for the EQ-5D-5L will be provided by treatment group. • For the MMRM analyses of change from baseline in HRQoL parameters, an LSMEANS statement will provide adjusted treatment group means and standard errors and a point estimate and two-sided 95% confidence interval for the adjusted mean treatment difference

Patient Reported Outcomes Statistical Analyses: HRQoL and Utility Score
(daprodustat - darbepoetin alfa) and a one-sided superiority p-value for this test at Weeks 8, 12, 28, and 52 for the SF-36 component scores and domains, and at Week 52 for the EQ-5D-5L and EQ VAS.
Model Results Interpretation

 One-sided p-values will be compared to 0.025 to assess nominal significance. Clinically meaningful effects for PRO assessments focused on metrics that would be needed for a reimbursement agency or health technology assessment agency will be specified in a separate reimbursement RAP.
Subgroup Analysis

 Subgroup analyses will be performed for the change from baseline in the SF-36 PCS, MCS, vitality and physical functioning domains at Week 28 and 52 using the age and gender subgroups only (described in Section 10.10) in a method similar to that described for the subgroup analysis of the secondary Hgb change from baseline analyses.

